## 10. Study Methods

### 10.1. *Data Collection*

This section indicates the data needed to fulfill the objectives of this clinical study. Boston Scientific Corporation considers data collected from clinical trial subjects to be personal data (see definitions of different data categories in **Table 25.2-1**) and compliance with privacy and data protection laws and regulations (for example, the General Data Protection Regulation [GDPR], see **Table 25.2-1**) to be critically important. Data collection for this clinical study has been carefully considered to comply with data privacy laws.

The data collection schedule is shown in **Figure 10.1-1** and in **Table 10.1-1**. Additional information is provided in Section **10.2** through Section **10.9**. The methods are based on NeuroARC metrics, VARC metrics, and/or guideline recommendations.

**Figure 10.1-1: PROTECTED TAVR Study Event Schedule**

See Table 10.1-1 for additional information.

Abbreviations: ADE=adverse device effect; CAM-ICU=Confusion Assessment Method for Intensive Care Unit Patients; CEC=Clinical Events Committee; CPS=cerebral protection system; CT=computed tomography; MoCA=Montreal Cognitive Assessment; NIHSS=National Institutes of Health Stroke Scale; SADE=serious adverse device effect; SAE=serious adverse event; UADE=unanticipated adverse device effect; USADE=unanticipated serious adverse device effect; TAVR=transcatheter aortic valve replacement

**Table 10.1-1: PROTECTED TAVR Study Event Schedule**

Assessment	Baseline a	Index Procedure	≤72 Hours / Discharge	30±7 Days Post Stroke b
Signed Informed Consent Form	X	–	–	–
Clinical Assessments				
Demographics and medical history	X	–	–	–
Physical assessment	X	–	–	–
Risk assessment c	X	–	–	–
Imaging Assessments				
Anatomic suitability for the Sentinel device d	X	–	–	–
Neurological Assessments e				
Neurological physical examination f	X	–	X	–
Modified Rankin Scale score g	X	–	X	X b
NIHSS g	X	–	X	–
CAM-ICU h	X	–	X	–
MoCA i	X	–	X	–
Quality of Life Survey j	X			
Adverse event assessment	–	X k	X k	X b

**Note 1:** X = should be performed, – = not required.

a: Within 30 days prior to index procedure (unless otherwise specified).

b: In all subjects where stroke is suspected, a formal neurology/stroke consult should be obtained, and the subject should be further assessed and treated per standard of care. In subjects diagnosed with post-procedural stroke, mRS must also be administered at 30±7 days after the stroke; the simplified mRS questionnaire may be used for this follow-up evaluation. In these subjects, mortality and an assessment of device related adverse events (ADE, SADE, UADE, and USADE; see **Table 25.2-1** for definitions) must be reported to BSC from the time of enrollment through 30±7 days post stroke.

c: Data from the STS risk score assessment must be collected (see definition of surgical risk in **Table 25.2-1**); euroSCORE II risk score data may be collected if performed per local standard of care; height and weight must be collected (to determine body mass index).

d: Anatomic assessment must be carried out using CT or per local standard of care to determine if subject has the recommended artery diameter at the site of filter placement per the study Inclusion Criteria (**Table 8.1-1**).

e: Follow-up neurological assessments must be performed within 72 hours post index procedure but may be performed earlier if deemed necessary. These post-procedure assessments should be performed only when the subject is no longer drowsy from procedural medication.

f: Assessment must be carried out by a neurology professional (board certified/board eligible neurologist, neurology fellow, neurology physician assistant, or neurology nurse practitioner).

g: Assessment must be carried out by certified personnel.

h: The Confusion Assessment Method for ICU Patients (CAM-ICU) should be done at baseline and on day 1 post procedure; it must be performed by personnel with appropriate training as documented by the sponsor.

i: The Montreal Cognitive Assessment (MoCA) must be carried out by certified personnel.

j: EQ-5D questionnaire is conducted at baseline

k: The adverse event assessment includes SAE, ADE, SADE, UADE, USADE, device deficiencies, and CEC events; safety events will be monitored and reported to BSC from the time of enrollment through 72 hours or subject discharge (whichever comes first). Please refer to Section **19.1** for reportable events,

**Table 10.1-1: PROTECTED TAVR Study Event Schedule**

Assessment	Baseline a	Index Procedure	≤72 Hours / Discharge	30±7 Days Post Stroke b
------------	-----------------------	-----------------	-----------------------	------------------------------------

including a list of CEC events, and to **Table 25.2-1** for definitions of these events, which specify data required for CEC adjudication.

Abbreviations: ADE=adverse device effect; BSC=Boston Scientific Corporation; CAM-ICU=Confusion Assessment Method for Intensive Care Unit Patients; CEC=Clinical Events Committee; CT=computed tomography; MoCA=Montreal Cognitive Assessment; mRS=modified Rankin Scale; NIHSS=National Institutes of Health Stroke Scale; SADE=serious adverse device effect; SAE=serious adverse event; STS=Society of Thoracic Surgeons; UADE=unanticipated adverse device effect; USADE=unanticipated serious adverse device effect

**10.2. Study Subject Screening**

Subjects will be evaluated for eligibility for commercial TAVR by the center heart team per the local standard of practice. Subjects with documented aortic valve stenosis who are to be treated with a commercially available TAVR device and who sign the IRB/IEC/HREC-approved ICF will be assessed for enrollment in the clinical study. Inclusion and exclusion criteria are provided in Section 8. Every subject must be deemed treatable with the Sentinel study device.

Once written informed consent has been obtained, a subject will be entered into a screening log, which will be maintained at the center. A subject who provides written informed consent will be entered into the screening log whether or not the subject is randomized into the study. For consented subjects not enrolled in the trial, the reason for screen failure will be documented in the screening log.

It is estimated that nearly 5% of elderly ≥75 years of age have aortic stenosis and its prevalence is expected to increase due to an aging population. Because aortic stenosis most commonly occurs in the very elderly, women are well represented in TAVR studies. As the very elderly will represent the majority of enrolled subjects, traditionally underrepresented populations are expected to be included in the subject population as allowed by governing law/national regulation.

**10.3. Subject Informed Consent**

Written informed consent (see Section 20) must be obtained for all qualified subjects who are potential study candidates prior to the subject’s index procedure.

The Investigator/designee who has been trained on the protocol will explain the nature and scope of the study, potential risks and benefits of participation, and answer questions for the subject. If the subject agrees to participate, the IRB/IEC/HREC-approved ICF must be signed and personally dated by the subject or his/her legally authorized representative. The Investigator/designee must also sign the ICF prior to subject enrollment. Any additional persons required by the center’s IRB/IEC/HREC to sign the ICF must also comply.

#### 10.4. Baseline Assessments

The following assessments must be completed within 30 days prior to the index procedure per local standard of care for TAVR unless otherwise indicated. The study electronic case report forms (eCRFs) identify the specific data points to be collected.

- Confirmation of eligibility and contraindications per the Sentinel® Cerebral Protection System IFU (see **Note 1** below)
- Clinical assessments
  - Demographics including age and gender
  - Medical history
  - Physical assessment
  - Risk assessments
    - Society of Thoracic Surgeons (STS) risk score
    - EuroSCORE II (if performed per local standard of care)
    - Nutritional assessment (height and weight)
- Imaging assessments
  - Anatomic suitability for the Sentinel device (computed tomography [CT] assessment as performed per local standard of care)
- Neurological assessments
  - Neurological physical exam (see **Note 2** below)
  - mRS score (see **Note 2** below)
  - NIHSS score (see **Note 2** below)
  - CAM-ICU (see **Note 3** below)
  - MoCA (see **Note 4** below)
- Quality of Life Survey (EQ-5D) should be administered within 30 days prior to the procedure

**Note 1:** Every subject must be deemed treatable with the Sentinel device (have suitable anatomy per the IFU).

**Note 2:** The neurological physical exam must be performed by a neurology professional (board certified/board eligible neurologist, neurology physician assistant, or neurology nurse practitioner). The NIHSS and mRS must be performed by certified personnel (external certification for NIHSS; internal or external certification for mRS).

**Note 3:** The delirium assessment consists of the Confusion Assessment Method for ICU Patients (CAM-ICU) and must be performed by personnel with appropriate training as documented by the sponsor.

**Note 4:** The cognitive assessment consists of the Montreal Cognitive Assessment (MoCA) and must be carried out by certified personnel (external certification).

### 10.5. *Index Procedure*

The preparation of the subject for the percutaneous procedure will be performed following standard techniques. Refer to the Sentinel IFU for instructions on preparation and use of the cerebral protection system test device. Refer to the specific valve Directions/Instructions For Use for instructions on preparation and placement of the commercial TAVR valve. Subject randomization will occur prior to procedural puncture/incision; see Section 11.2.4 for information on stratification. Study device deficiencies and safety events during the procedure (includes SAE, SADE, UADE, USADE, ADE, and CEC events; see Section 19) along with the associated treatment must be reported to BSC. The end of the index procedure is defined as vessel closure and hemostatic control.

**Note 1:** Use of general anesthesia during TAVR may affect neurocognitive function shortly after the procedure. While not an exclusion criterion, it is recommended that general anesthesia not be used if possible.

### 10.6. *Post-Procedure (≤ 72 Hours)/Prior to Hospital Discharge*

Within 72 hours post TAVR procedure or before discharge (whichever comes first), the following neurological assessments must be performed (see **Note 1** below).

- Neurological physical exam (see **Note 2** in Section 10.4 and **Note 2** below)
- mRS score (see **Note 2** in Section 10.4 and **Note 2** below)
- NIHSS score (see **Note 2** in Section 10.4 and **Note 2** below)
- CAM-ICU (see **Note 3** in Section 10.4 and **Note 3** below)
- MoCA (see **Note 4** in Section 10.4)

**Note 1:** Follow-up neurological assessments must be performed within 72 hours post TAVR procedure but may be performed earlier if deemed necessary. These post-procedure assessments should be performed only when the subject is no longer drowsy from procedural medication. The neurological assessor should be blinded to the subject's cerebral protection device treatment group.

**Note 2:** In all subjects where stroke is suspected, a formal neurology/stroke consult should be obtained, and the subject should be further assessed and treated per standard of care. In subjects diagnosed with post-procedural stroke, mRS must also be administered at 30±7 days following the stroke (see Section 10.7 below). The simplified mRS questionnaire may be used for this follow-up assessment.

**Note 3:** This delirium assessment should be done on day 1 post TAVR procedure.

A complete safety event assessment, including any SAE, ADE, SADE, UADE, USADE, device deficiency with associated treatment, and any CEC event regardless of seriousness and device relationship (see Section 19) must be carried out and reported to BSC from the time of enrollment through 72 hours post TAVR procedure or subject discharge (whichever

comes first). Please see Section 10.7 below for additional information regarding subjects with stroke.

The subject may be discharged from the hospital when clinically stable, at the Investigator's discretion per local standard of care. Pharmacologic management of subjects in both treatment groups, including antiplatelet and anticoagulant medications, is left to the discretion of the treating physician.

### 10.7. *Post-Stroke (30±7 Days)*

In all subjects where stroke is suspected ( $\leq 72$  hours post TAVR procedure or through discharge, whichever comes first), a formal neurology/stroke consult should be obtained, and the subject should be further assessed and treated per standard of care. In subjects diagnosed with post-procedural stroke, mRS must also be administered at 30±7 days after the stroke. The simplified mRS questionnaire may be used for this follow-up assessment. For subjects with stroke, mortality plus device related adverse events (ADE, SADE, UADE, and USADE; see **Table 25.2-1** for definitions) through 30±7 days post stroke must be reported to BSC.

### 10.8. *Study Completion*

All subjects will be followed through 72 hours post TAVR procedure or hospital discharge (whichever comes first). A subject's participation in the study will be considered complete after 72 hours or hospital discharge (whichever comes first). See Section 10.7 regarding additional follow-up for subjects who experience a stroke. For those subjects, study duration will be through 30±7 days after the stroke.

### 10.9. *Source Documents*

It is preferable that original source documents, when available, are maintained at the investigative center. In lieu of original source documents, certified copies are required to be maintained. A certified copy is a copy (irrespective of the type of media used) of the original record that has been verified (i.e., by a dated signature or by generation through a validated process) to have the same information, including data that describe the context, content, and structure, as the original. Source documentation includes but is not limited to those items noted in **Table 10.9-1**. Source documentation provided to the Sponsor for assessment/adjudication will be deidentified per local law and regulations.

**Table 10.9-1: Source Documentation Requirements**

Requirement	Disposition
Printed, optical, or electronic document containing source data. Examples may include but are not limited to: hospital records, laboratory notes, device accountability records, photographic negatives, radiographs, records kept at the investigation center, at the laboratories and at the medico-technical departments involved in the clinical investigation.	Retain at center.

**Note:** Please see **Table 25.2-1** for definitions of "source data" and "source document."

## 11. Statistical Considerations

### 11.1. Endpoints

#### 11.1.1. Primary Endpoint

The study is powered to assess the primary endpoint, which is all stroke (hemorrhagic, ischemic, or undetermined status; disabling or nondisabling) through 72 hours post TAVR procedure or hospital discharge (whichever comes first) as adjudicated by an independent CEC using NeuroARC definitions.

##### 11.1.1.1. Statistical Hypothesis for the Primary Endpoint

The primary statistical hypothesis is that the rate of the primary endpoint (all stroke through 72 hours post TAVR procedure or discharge [whichever comes first]) in the Sentinel (Test) cohort is superior to that in the Control cohort. The null and alternative hypotheses for the primary endpoint are as follows:

$$H_0: P_{\text{Sentinel}} = P_{\text{Control}}$$

$$H_1: P_{\text{Sentinel}} \neq P_{\text{Control}}$$

where  $P_{\text{Sentinel}}$  and  $P_{\text{Control}}$  correspond to the rates of the primary endpoint for the Sentinel cohort (test) and the Control cohort (no cerebral protection), respectively.

Testing will be done for the primary endpoint as described in the statistical analysis plan. A chi-square test will be used. The primary analysis population for the primary endpoint is the ITT analysis set; this endpoint will also be analyzed for the Per-Protocol analysis set (see Section 11.2.1 for description of analysis sets).

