	
EC6. Subject is contraindicated for anticoagulant and antiplatelet therapy.
 
Note 4: Use of general anesthesia during TAVR may affect neurocognitive function shortly after the procedure. While not an exclusion criterion, it is recommended that general anesthesia not be used if possible.

Adjunctive Pharmacologic Therapy	Management of subjects in both groups, including antiplatelet and anticoagulant medications, is left to the discretion of the treating physician.
Statistical Methods	
Analysis Sets	
Analysis sets are listed below.
 
Intention-To-Treat (ITT): This population includes all subjects who sign an ICF and are enrolled in the trial (randomized), whether or not the assigned treatment is received.
 
Per-Protocol: This population includes all ITT subjects who undergo TAVR and who are treated as assigned in the randomization process (excludes crossovers).

Statistical Hypothesis for the Primary Endpoint	The rate of the primary endpoint (all stroke through 72 hours post TAVR procedure or hospital discharge [whichever comes first] as adjudicated by an independent CEC) in the Sentinel (Test) cohort is superior to that in the Control cohort.
Statistical Test Method for the Primary Endpoint	
A chi-square test will be used to test the two-sided hypothesis of superiority of Sentinel versus the Control:
 
<math>H_0: P_{\text{Sentinel}} = P_{\text{Control}}</math>
 
<math>H_1: P_{\text{Sentinel}} \neq P_{\text{Control}}</math>
 
where <math>P_{\text{Sentinel}}</math> and <math>P_{\text{Control}}</math> correspond to the rates of the primary endpoint for the Sentinel group (test) and the Control group (no cerebral protection), respectively.
 
The primary analysis set is the ITT analysis set; this endpoint will also be analyzed for the Per-Protocol analysis set.

Sample Size Parameters for the Primary Endpoint	
Sample size parameters are listed below.
 
 
• Expected Control rate <math>P_{\text{Control}}</math>: 4%
 
• Expected Sentinel (test) rate <math>P_{\text{Sentinel}}</math>: 2% (50% relative reduction)
 

PROTECTED TAVR: Stroke PROTEction with SEntinel During Transcatheter Aortic Valve Replacement	

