### 7.1. Scale and Duration

An initial enrollment of up to 3000 randomized subjects in up to 100 study centers is planned (see **Note 1** below). A single center may enroll up to 15% of the total enrollment; approval from the Sponsor is required for additional enrollment. Subjects to be treated via a transfemoral approach with a commercially available TAVR device will be randomized 1:1 into a Test cohort using the commercially available Sentinel or a Control cohort with no cerebral protection system. A subject who provides an ICF signed by the subject or the subject’s legally authorized representative is considered enrolled in the study upon randomization, which will occur at the index procedure prior to procedural puncture/incision. The study duration for each subject is expected to be through 72 hours or hospital discharge, whichever comes first. In subjects diagnosed with a stroke, mRS must be administered at 30±7 days after the stroke. For these subjects, study duration will be through 30±7 days post stroke.

**Note 1:** If sample size re-estimation is needed (see Section **11.1.1.2**), the planned maximum enrollment will be up to 6000 randomized subjects.

**Figure 7.1-1** summarizes the study design. The treating physician must be a trained, experienced Sentinel user. Every subject must be deemed treatable with the Sentinel device (have suitable anatomy per the Sentinel Instructions For Use [IFU]). All eligible subjects (see Section **8**) should be approached for participation in the trial.

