## 7.2. Treatment Assignment

Subjects who are to be treated with a commercially available TAVR device and who have suitable anatomy for the Sentinel device will be randomized 1:1 into a Test cohort using the commercially available Sentinel or a Control cohort with no cerebral protection system. Randomization will occur at the index procedure (prior to procedural puncture/incision) to avoid selection/treatment bias. The randomization schedules will be computer-generated, using a pseudo-random number generator. Randomization will be stratified by center, by operative risk, and by intended TAVR valve type (Section 11.2.4). All randomized subjects will have unique identification numbers. Random permuted blocks will be employed to ensure approximate balance of treatment allocation within each stratum. Instructions on randomization are provided in the Manual of Operations. See Section 5 for a detailed description of the Sentinel device.

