#### 11.1.1.3. Success Criteria for the Primary Endpoint

As noted above, 1 planned formal interim analysis for the primary endpoint will be conducted on the first 70% of enrolled subjects and a final analysis will be conducted on all enrolled subjects if the study is not stopped after the interim analysis. The alpha-level for the interim analysis and the final analysis is adjusted using the Lan-Demets spending function with O'Brien-Fleming boundaries as detailed below in Section 11.3.2. If the *P* value from the chi square test is less than alpha and the rate in the Sentinel group is less than the rate in the Control group, the group with Sentinel will be concluded to have a lower rate of all stroke through 72 hours post TAVR procedure or hospital discharge (whichever comes first) compared to the Control group.

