### 11.2.4. Randomization Scheme

Using a computer-generated list of random treatment allocations (i.e., a randomization schedule) subjects to be treated with a commercially available TAVR device will be randomized 1:1 into a Test cohort using the commercially available Sentinel device or a Control cohort with no cerebral protection system. Randomization will be stratified by center, by operative risk (low risk and intermediate or higher risk; see surgical risk definitions in Table 25.2-1), and by intended TAVR valve type (balloon-expandable device and non-balloon expandable device). Additional information is provided in the study Manual of Operations.

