### 11.3.2. Interim Analyses

One formal interim analysis is planned for the purpose of stopping this trial early for effectiveness. This analysis will be performed by the Independent Safety and Statistical Monitor (see Section 21.3). The interim analysis for the primary endpoint will be conducted on the first 70% of enrolled subjects; a final analysis will be conducted on all enrolled subjects if the study is not stopped after the interim analysis.

The Lan-Demets spending function with O'Brien-Fleming boundaries is used to adjust the alpha-level for the interim analysis and the final analysis (if needed): 0.0148 and 0.0455, respectively. If the *P* value from the chi-square test is less than alpha, and the rate in the Sentinel group is less than the rate in the Control group, the group with Sentinel will be concluded to have a lower rate of all stroke through 72 hours post TAVR procedure or discharge (whichever comes first) versus the Control group and the study will be stopped. If the study is not stopped after the interim analysis, sample size re-estimation may be performed contingent on the results of the interim analysis (see Section 11.1.1.2).

The planned interim analysis is pre-specified to provide a formal hypothesis testing approach to examine the primary endpoint with the adjusted significance level and stop the trial early for effectiveness if appropriate. This pre-specified interim analysis allows for sample size re-estimation per the study's adaptive group sequential design.

Additional analyses not defined in the protocol may also be conducted for regulatory agency review.

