### 11.3.4. Justification of Pooling

Analyses for the primary endpoint will be presented using data pooled across centers and intended TAVR valve types. An assessment of the poolability of subjects across centers and intended TAVR valve types will be made using logistic regression. Main effects for the center (intended TAVR valve type) and treatment and the interaction of the center (intended TAVR valve type) by treatment will be included in separate logistic regression models with the primary endpoint as the outcome. If the *P* value for center (intended TAVR valve type) by treatment interaction is  $\geq 0.1$ , it can be concluded that the treatment effect is not different across the centers (intended TAVR valve types) and the data can be pooled. In the analysis to justify pooling across centers, the centers with fewer than 10 subjects enrolled in the study

will be combined into “virtual centers” based on geographic region so that “virtual centers” have  $\geq 10$  subjects but no more than the largest enrolling center.

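### Randomization is stratified, but the primary test at both looks is an unstratified chi-square: valid, slightly conservative if the strata predict stroke, and cheap to improve

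*Combined protocol and SAP*

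**What the plan says.** Section 7.2 describes the allocation: "Random permuted blocks will be employed to ensure approximate balance of treatment allocation within each stratum". Section 11.2.4 names the factors: "Randomization will be stratified by center, by operative risk (low risk and intermediate or higher risk"), and intended valve type, balloon-expandable or not.

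The synopsis names the test: "A chi-square test will be used to test the two-sided hypothesis of superiority of Sentinel versus the Control". Section 11.1.1.1 repeats it: "A chi-square test will be used. The primary analysis population for the primary endpoint is the ITT analysis set". The decision rules use the same test. At the interim look, Section 11.3.2 makes success depend on this condition for the P value and the direction: "chi-square test is less than alpha, and the rate in the Sentinel group is less than the rate in the Control group"; Section 11.1.1.3 states the same condition in general.

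Section 11.3.4 adds: "Analyses for the primary endpoint will be presented using data pooled across centers and intended TAVR valve types". Its logistic models only judge whether the treatment effect differs by center or valve type. Section 11.3.3 adds a treatment-by-risk interaction as a subgroup analysis. Neither supplies a stratified test of the treatment effect. Section 11.1.1.1 also refers to a statistical analysis plan for the testing; no separate plan is reproduced in the document reviewed.

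**The concern.** Blocking within strata makes the arms alike on the stratification factors. Where those factors predict stroke, the difference in stroke rates then varies less from trial to trial than under simple randomization. The pooled chi-square does not know this. It uses the variance for simple randomization, which is too large, so its actual type I error falls below the nominal level and some power is lost.

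The error is on the safe side and no false claim of benefit is at stake. What is at stake is a little power, mostly at the interim look, that the trial has already paid for by stratifying.

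**Working it through.** **Inputs from the plan.** Control rate 4%, Sentinel rate 2%, two-sided alpha 0.05, 1:1 allocation, N = 3000, interim at N = 2100 (Section 11.1.1.2); nominal levels 0.0148 and 0.0455 (Section 11.3.2); two levels each of operative risk and valve type (Section 11.2.4).

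**Assumed.** The plan does not say how strongly the strata predict stroke. I use four equal strata and write the risk ratios as operative risk x valve type: 1x1 (no effect), 2x1.5, 3x2 and 4x3.

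**1. The plan's own figures.** O'Brien-Fleming-type Lan-DeMets spending at information fraction 0.70 gives 4[1 − Φ(2.2414/√0.70)] = 4[1 − Φ(2.679)] = 0.01477. The final level, from the bivariate normal with correlation √0.70, is 0.04551. Both round to the stated 0.0148 and 0.0455. By normal approximation, power at N = 3000 without re-estimation is 89.1% over the two looks. With re-estimation to 6000 it is 91.0% to 92.6%, if the promising zone is assumed to start at conditional power 0.50 to 0.30 (the rule is in the charter). That agrees with the stated power above 0.90, which is not in question.

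**2. Conservatism by formula.** For strata with weights w_s and null risks p_s averaging p, and arms balanced within strata:

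- variance ratio = 1 − Σ w_s(p_s − p)² / [p(1 − p)]
- actual level = 2[1 − Φ(z / √ratio)]

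For 4x3 the multipliers are 1, 4, 3 and 12, with mean 5. At p = 4% the risks are 0.8%, 3.2%, 2.4% and 9.6%. The between-stratum variance is 0.00272 − 0.00160 = 0.00112, and 0.00112/0.0384 = 0.029, so the ratio is 0.971.

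- Final: 2.000/√0.971 = 2.030, level 0.0424 instead of 0.0455.
- Interim: 2.437/√0.971 = 2.473, level 0.0134 instead of 0.0148.

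**3. Simulation, chi-square versus CMH.** One million trials per scenario, exact balance within the four strata, cumulative data at 2100 and 3000, no continuity correction. Size is at equal rates (4% on average in both arms); power is at 4% versus 2%.

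| Strata | Final size | Final power | Stop at interim, true effect |
|---|---|---|---|
| 1x1 | 0.0454 vs 0.0454 | 0.895 vs 0.895 | 0.604 vs 0.602 |
| 2x1.5 | 0.0448 vs 0.0457 | 0.895 vs 0.896 | 0.605 vs 0.608 |
| 3x2 | 0.0435 vs 0.0453 | 0.896 vs 0.898 | 0.605 vs 0.613 |
| 4x3 | 0.0423 vs 0.0455 | 0.898 vs 0.902 | 0.605 vs 0.615 |

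Type I error over both looks runs from 0.0499 vs 0.0498 (1x1) to 0.0465 vs 0.0500 (4x3). In separate runs of 400,000 trials, overall power was 0.8979 vs 0.8978 (1x1), 0.8981 vs 0.8986 (2x1.5), 0.8983 vs 0.9004 (3x2) and 0.9004 vs 0.9042 (4x3). Over both looks the chi-square won a trial that CMH lost in at most 8 per 100,000 (1x1) and in none at 3x2 or 4x3. CMH won a trial that the chi-square lost in 0.2% (3x2) to 0.4% (4x3) under the true effect.

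**4. Unequal strata and incomplete blocks.** With 35% of subjects in each higher-rate category at 3x2, final size is 0.0431 vs 0.0453 and power 0.896 vs 0.899. Incomplete blocks were checked over 100 centers x 2 x 2 strata with an assumed block size of 4, both factors at risk ratio 2 and a 3% overall rate. The chi-square level at nominal 0.05 was 0.0493, against 0.0492 with perfect balance.

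**5. Why not stratify by center too.** Section 7.1 states: "An initial enrollment of up to 3000 randomized subjects in up to 100 study centers is planned". So 100 x 4 = 400 cells, 3000/400 = 7.5 subjects per cell, and 7.5 x 3% = 0.225 strokes per cell. Four equal risk-by-valve strata hold 750 subjects and 750 x 3% = 22.5 strokes each.

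**The case against.** The strongest reply is that this is a preference. The chi-square is valid and named consistently, the pooling is stated openly, and the stated power holds. The gain is small: the 0.4-point figure needs a 12-fold stroke-risk gap between the lowest and highest stratum, and at 2x1.5 the overall gain is about 0.05 points. With uninformative strata, CMH stops early slightly less often (0.602 vs 0.604). The proposed test still omits center, so it does not fully follow the randomization. A stratified supportive analysis may already exist in a separate analysis plan, and the re-estimation rule, which sits in the charter, was not modelled.

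All of this is accurate, and it limits the point to a small efficiency gain. It does not reverse the balance. The loss with flat strata is almost entirely recovered by the final look, whereas informative strata bring a gain at both looks. Omitting center has a sound reason in the sparse cells; any conservatism from differences between centers would remain, and is not sized here. A supportive analysis elsewhere would not change the test that decides success.

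**Conclusion.** The point holds as an inexpensive improvement that should be made; it is not a validity defect. The primary test ignores factors on which the trial is randomized. Under the assumed range the cost is an overall type I error of 0.0465 to 0.050 where 0.050 is allowed, 0 to 0.4 points of overall power, and a change in the chance of early stopping for a true effect from about −0.2 points (flat strata) to +1.0 point (4x3). The direction of the conservatism is certain if operative risk or valve type predicts stroke. Its size is assumed, because the documents give no stroke rates by stratum. The figures apply to the two planned looks without sample size re-estimation.

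**What to change.** - Make the primary test at both looks a CMH test without continuity correction, stratified by operative risk (low; intermediate or higher) and intended valve type (balloon-expandable; not), as randomized. Keep the levels 0.0148 and 0.0455.
- Report the Mantel-Haenszel risk difference with its confidence interval, and use its sign for the direction condition.
- Keep the unstratified chi-square as a prespecified sensitivity analysis.
- State that center is left out of the test because its cells are sparse.
- Align the synopsis, Sections 11.1.1.1, 11.1.1.3 and 11.3.2, the statistical analysis plan and, where it names the test statistic, the Independent Safety and Statistical Monitor charter.

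The cost is wording, all of it before the interim analysis. Both factors are already recorded at randomization, so no new data are needed, and sample size and alpha levels stay as they are.
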